Appendix C

The HES OPCS 4.7 codes that will be used are shown below. These codes have been provided to the lead applicant by the Expert Advisor in Orthopaedics to the Clinical Classifications Service HSCIC (Health and Social Care Information Centre) and Designated Centre for WHO FIC (Family of International Classifications Network). The codes are based on the following procedures “labral repair, stabilisation, capsular shift, Laterjet, bone transfer, SLAP repair and Bankart repair”. For any codes that do not define anatomical site, the following site codes should be present Z81.3 (Glenohumeral Joint) or Z81.4 (Shoulder Joint). The codes in *italics* are usually used for other joints such as the acromio-clavicular joint but we have been informed they are often used for shoulder stabilisation of the glenohumeral joint and will therefore need to be included in the analysis during linkage to CPRD shoulder dislocation codes.

HES OPCS 4.7 CODES.

Operative Description	OPCS 4.7 Codes
Stabilising operations on joint	W77
Repair of capsule of joint for stabilisation of joint NEC	W77.1
Transposition of muscle for stabilisation of joint	W77.2
Blocking operations on joint using prosthesis for stabilisation of joint	W77.3
Blocking operations on joint using bone for stabilisation of joint	W77.4
Periarticular osteotomy for stabilisation of joint	W77.5
Transposition of ligament for stabilisation of joint	W77.7
Other specified stabilising operations on joint	W77.8
Unspecified stabilising operations on joint	W77.9
Prosthetic replacement of ligament	W72
Primary prosthetic replacement of multiple ligaments	W72.1
Prosthetic replacement of multiple ligaments NEC	W72.2
Primary prosthetic replacement of intra-articular ligament	W72.3
Prosthetic replacement of intra-articular ligament NEC	W72.4
Primary prosthetic replacement of extra-articular ligament	W72.5
Prosthetic replacement of extra-articular ligament NEC	W72.6
Other specified prosthetic replacement of ligament	W72.8
Unspecified prosthetic replacement of ligament	W72.9
Other stabilising operations on joint	O27
Extra-articular ligament reconstruction for stabilisation of joint	O27.1

Repair of capsule and anterior and posterior labrum for stabilisation of glenohumeral joint	O27.2
Repair of capsule and anterior labrum for stabilisation of glenohumeral joint	O27.3
Repair of capsule and posterior labrum for stabilisation of glenohumeral joint	O27.4
Other reconstruction of ligament	W74
Reconstruction of multiple ligaments NEC	W74.1
Reconstruction of intra-articular ligament NEC	W74.2
Other specified other reconstruction of ligament	W74.8
Unspecified other reconstruction of ligament	W74.9
Other open repair of ligament	W75
Open repair of multiple ligaments NEC	W75.1
Open repair of intra-articular ligament NEC	W75.2
Open repair of extra-articular ligament NEC	W75.3
Other specified other open repair of ligament	W75.8
Unspecified other open repair of ligament	W75.9
Therapeutic endoscopic operations on other joint structure	W84
Endoscopic repair of intra-articular ligament	W84.1
Endoscopic reattachment of intra-articular ligament	W84.2
Endoscopic repair of superior labrum anterior to posterior tear	W84.7
Other specified therapeutic endoscopic operations on other joint structure	W84.8
Unspecified therapeutic endoscopic operations on other joint structure	W84.9
Capsulorrhaphy of joint	W81.6

APPENDIX D

TABLE OF CPRD DISLOCATION READ CODES

Description	READ Code	Number of clinical events currently recorded in CPRD
Dislocation or subluxation of shoulder	S41.00	51,162
Dislocation of shoulder NOS	S41z.00	11,578
H/O: dislocated shoulder	14G5.00	6,724
Closed reduction of dislocation of shoulder	7K6G300	2,878
Closed traumatic dislocation of shoulder	S410.00	2,240
Recurrent dislocation of shoulder – anterior	N083A00	2,140
Anterior dislocation of shoulder	S410111	1,864
Recurrent joint dislocation, of shoulder region	N083100	1,321
Recurrent subluxation of shoulder – anterior	N083C00	599
Closed traumatic dislocation shoulder jnt. Anterior (sub-coracoid)	S410100	439
Closed traumatic dislocation shoulder joint, unspecified	S410000	439
Closed traumatic subluxation, shoulder	S412.00	288

APPENDIX E

Table of Expert Consensus List of Risk Factors.

Risk factors for re-dislocation after first dislocation	Risk factors for re- dislocation after surgery
Age	Age
Gender	Gender
UK Region	UK Region
Deprivation Scores	Deprivation Scores
Glenoid and / or Humeral Bone loss	Glenoid and / or Humeral Bone loss
Mechanism of injury	Number of dislocations pre-surgical repair
Rotator cuff tears	Time between first dislocation and surgery
Imaging findings	Anterior apprehension
Anterior apprehension	Occupation
Occupation	Sport type and level
Sport type and level	Operation type
Neurological injury	Laxity/Beighton Score
Laxity/Beighton Score	Insufficient physio / rehab after surgery
Insufficient physio / rehab after first dislocation	Time for return to sports
Young Rugby player under 20	Number of anchors used at surgery
Time at return to sports	Incorrect positioning of anchors
Post dislocation immobilisation	Not addressing capsular laxity at surgery
	Previous lower limb or back injury

This project was funded by the National Institute for Health Research Health Technology Assessment (project number 14/160/01).

The views and opinions expressed therein are those of the authors and do not necessarily reflect those of the HTA, NIHR, NHS or the Department of Health.

APPENDIX F

METHOD FOR LINKAGE OF CPRD AND HES DATASETS

CPRD data is linked to HES using the HESID identifier. Over 60% of the CPRD population is currently linked to HES. The linkage of CPRD to HES data is a 2-step process: (1) The creation of a unique and anonymous ID in HES for each patient (HESID), and (2) Linkage of CPRD to HES using the HESID index. The detailed protocol on creating a HESID is publicly available online (http://www.hscic.gov.uk/media/1370/HES-Hospital-Episode-Statistics-Replacement-of-the-HES-patient-ID/pdf/HESID_Methodology.pdf).

In summary the majority of hospital admission episodes are linked using a combination of sex + date of birth (dob) + NHS number (step 1) OR sex + dob + [postcode + local hospital generated patient identifier] (step 2). Since 2009 a third step was added to try and increase the linkage in early years where NHS number was less completely recorded. This allows for a match on sex + dob + postcode, but only where this does not lead to a HESID being associated with 2 different NHS numbers, and only where the postcode is not on the list of known communal establishments (nursing homes, army barracks, prisons). In the past 10 years, NHS number has been complete for >95% of all records so the HESID should be particularly reliable during this period. Efficiency of the HESID algorithm may have been lower in earlier years when the completeness of recording of NHS number was lower.

Linkage CPRD-HES using the HESID: HES use a standard 8 pass algorithm to link HES to CPRD data via the HESID index (Detailed information is available online at http://www.hscic.gov.uk/media/11668/HES-ONS-Mortality-Data-Guide/pdf/guide_to_linked_ONS_HES_mortality_data_V4_040613.pdf).

The 8 passes involved are:

Pass 1 - Exact NHS, sex, DoB, Postcode

Pass 2 - Exact NHS, sex, DoB,

Pass 3 - Exact NHS, SEX, postcode, partial DOB

Pass 4 - Exact NHS, SEX, partial DOB

Pass 5 - Exact NHS, postcode

Pass 6 - Exact sex, dob and postcode (where NHS doesn't contradict the match, DOB not 1st of January & postcode not on the ignore list)

Pass 7 - Exact sex, DOB and postcode (where NHS doesn't contradict the match and dob is not 1st of January)

Pass 8 - Exact NHS

After this whole process, CPRD only keeps matches that are identified in passes 1 through 5. This means that the match must be on NHS number plus at least one other piece of information (and in most cases 2 other pieces).

Given that the NHS number is available for 98-99% of CPRD patients, and for >95% of HES patients, the HES linkage methodology is considered very

[figure not shown]

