Using data from a Cochrane systematic review comparing surgical to non-surgical treatment for acute T ASD [6]; from the pooled results 3/58 patients in the surgical arm had subsequent further surgery (5.17%) compared to 17/61 in the non-surgical arm (27.9%) at a minimum follow up of 2-years (Risk Ratio 0.22, 95% CI 0.08 to 0.64). The large effect size is set in the context of the pooled results of 3 RCTs with uncertainty around the true size of the effect outside of a clinical trial setting in routine general practice. Conservatively, we would look to detect a smaller difference in subsequent surgery within 2-years of 25% in the non-surgical group, compared to 20% in the surgical group (an absolute difference of 5%). A 2-sided log rank test for equality of survival curves, with 90% power at 5% significance level (alpha), where outcome is time to re-dislocation, with an anticipated 25% re-dislocation rate in the non-surgical control group compared to a 20% in the surgical group (equivalent to a hazard ratio of 0.78), allowing for 10% loss to follow up and assuming equal group sizes, we require a total sample size of 3065 with 656 expected total of re-dislocations. There are 26,534 patients in CPRD with recurrent anterior shoulder dislocations, and at least 10,449 of these patients will be aged 16-35 years with T ASD [7]. The study will therefore be adequately powered. ***See flow diagram in appendix for estimation of numbers.***

H. Data Linkage Required (if applicable)

Data linkage and data management for our proposed study involves 2 different data sources (CPRD and HES). They need to be linked to answer the aims of WP2 as stated above. We have therefore included co-applicants with extensive experience in the use of linked datasets. The data management needed to produce a final working dataset will be carried out by a senior data manager at Oxford with expertise in such procedures. Under supervision from the application team, the data manager will develop ad-hoc code in Python and SQL to produce a dataset that can be analysed using standard statistical packages such as Stata.

I. Study Population

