The ***Intervention group*** will be patients in CPRD with first time T ASD who underwent shoulder stabilisation surgery after their first dislocation (early surgical repair in this NHS context will mean 'a decision to treat surgically after the first T ASD' and receiving surgery within 6 months). This means linking HES data to CPRD data in such a way that a HES surgical OPCS 4.7 code is seen to occur after a single first dislocation code in CPRD (without further dislocation codes) before that surgical date. The timelines between first dislocation codes and OPCS 4.7 codes will be recorded. The ***Control group***. While the most desirable control group would be physiotherapy, it is possible that WP1 will reveal that free text notes and referral codes on physiotherapy will be lacking and not reliable. If this is the case then conservative care will be defined as 'non surgical intervention' with no linked OPCS 4.7 surgical shoulder codes producing a control cohort of patients whose first time shoulder dislocation has been treated non-operatively. If however free text entries and referral codes for physiotherapy are reliably present in CPRD then conservative care will be physiotherapy identified by physiotherapy referral codes after a first time T ASD code. Any subsequent dislocation codes or OPCS 4.7 surgery code will be recorded.

K. Exposures, Outcomes and Covariates

As part of this application, we have performed a consensus survey of specialist shoulder surgeons and shoulder physiotherapists who are all members of the British Elbow and Shoulder Society. Saturation point and a list of predictors was reached rapidly and this list is tabulated in Appendix E and highlights the risk factors (and covariates) deemed most important. It is unlikely that all of these will be available from routinely collected national datasets but our study design will allow us to confirm through WP1 those factors that are reliably collected and that can be used for full analysis in WP2.

L. Data/ Statistical analysis

The association of surgical versus non-surgical intervention on subsequent re-dislocation within 2-years. The primary outcome of interest is the time from a first time traumatic anterior dislocation to subsequent re-dislocation within 2-years. The exposure of interest is whether or not a patient received shoulder surgery. In randomized controlled trials each person has

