As in the section above it is vital to deal adequately with confounding by indication. The team of applicants includes academic experts that have been leaders in the development of propensity scoring and prognostic modelling. In randomised controlled trials each person has an equal probability of being in a treatment or control group. Observational study designs are limited by an inherent imbalance of both known and unknown confounders making some patients more likely to receive surgery than others. As the type of surgery received is not randomly allocated in our study, confounding by indication will be accounted for by using propensity score matching methods. Use of these methods for the assessment of causality in epidemiological studies has been previously described[1]. The propensity score represents the probability that a patient received the intervention (surgery). A logistic equation is fitted where the outcome is actually the main study exposure (i.e. surgical intervention); and an agreed list of covariates (these have already been identified and listed in appendix E) are introduced as potential confounders of the study outcome, namely subsequent re-dislocation. This list has been pre-specified based on clinical knowledge, expert consensus and existing literature. Propensity scores are used then to match each patient receiving surgery to comparable non-surgical controls using a 0.02 standard deviations caliper as demonstrated in previous simulation studies [2]. This is a standard method for minimising confounding by indication, which not only provides participants with balanced baseline characteristics in both surgical and non-surgical groups, but also eliminates surgical patients with no comparable controls [3].

This methodology is now widely used in pharmaco-epidemiology and drug safety, and has both strengths and limitations. The main advantages of PS-matching are:

1. Exclusion of non-comparable subjects (eg non-surgical participants with a very low propensity score who probably have some contraindication or are not fit for surgery, and therefore should not be compared to those who actually underwent surgical repair).
2. This method produces clearly comparable cohorts in terms of observed confounders, and this is highly visual and intuitive.

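### HES linkage may have been weaker in earlier years, yet the protocol sets no calendar bounds on the cohort and leaves year of first dislocation out of the pre-specified propensity list

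*Protocol*

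**What the plan says.** Four parts of the protocol bear on this.

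- **Linkage (Appendix F).** NHS number is over 95% complete for the past 10 years. For the time before that, the text says "Efficiency of the HESID algorithm may have been lower in earlier years when the completeness of recording of NHS number was lower". It also reports an attempt to repair this: "Since 2009 a third step was added to try and increase the linkage in early years where NHS number was less completely recorded". CPRD keeps only link passes 1 to 5, each of which needs an exact NHS number.
- **Exposure (Sections F and J).** The surgical group needs a linked HES OPCS 4.7 code. If physiotherapy coding proves unreliable, the comparison group is patients with "no linked OPCS 4.7 surgical shoulder codes producing a control cohort".
- **Eligibility (Sections F and I).** The only time limits are relative: two years of CPRD data before the first dislocation code and two years after it. Patients must be linkable to HES. No calendar dates are set, and there is no stated requirement that HES cover the surgery window or follow-up.
- **Matching (Sections L and M).** The propensity model uses "an agreed list of covariates (these have already been identified and listed in appendix E"), described as pre-specified. Appendix E has age, gender, region, deprivation and clinical items. It has no calendar year.

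**The concern.** Appendix F raises era-dependent linkage as a possibility, and no other section deals with it. Section N expects no missing exposure data, and Section O says that all limitations are addressed elsewhere.

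Two separate problems could follow.

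1. **Confounding by era.** If recorded surgery is less frequent in early years, matched surgical patients come disproportionately from later years. If the recording of re-dislocation also changes over time, the two groups differ in baseline recorded risk for reasons unrelated to surgery. Year is available for every patient, so this is a measured confounder. Rosenbaum bounds are meant for unmeasured ones.
2. **Missed surgery.** A linkable patient whose early operation is not attached would be classed as non-surgical under the fallback definition. That dilutes the contrast.

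**Working it through.** **The plan's own figure.** Section G specifies "A 2-sided log rank test for equality of survival curves", "with 90% power at 5% significance level (alpha"), an "anticipated 25% re-dislocation rate in the non-surgical control group compared to a 20% in the surgical group", and "allowing for 10% loss to follow up and assuming equal group sizes".

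- Hazard ratio = ln(0.80)/ln(0.75) = 0.776 (stated as 0.78).
- Events: Schoenfeld 652, Freedman 659; stated 656.
- With exponential events and 10% exponential loss over two years, the event probabilities are 0.2379 and 0.1902, mean 0.2140. Then 656/0.2140 = 3065.

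The stated 3065 patients and 656 events reproduce and are not in dispute.

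**Inputs for the illustrations.** The 35% operated share is from Appendix B, and the 25% and 20% risks are from Section G. Capture rates and era-specific risks are assumptions, because the documents give none.

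**Missed surgery.** With capture c, the truly operated share of recorded controls is m = 0.35(1 − c)/(1 − 0.35c). Control risk becomes 0.25(1 − m) + 0.20m, and the observed hazard ratio is ln(0.80)/ln(1 − control risk).

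| Capture c | m | Control risk | Hazard ratio |
|---|---|---|---|
| 95% | 2.6% | 24.9% | 0.780 |
| 85% | 7.5% | 24.6% | 0.789 |
| 75% | 11.9% | 24.4% | 0.798 |
| 60% | 17.7% | 24.1% | 0.809 |

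At 3065 patients, power falls from 0.90 to 0.89 at 95% capture and to 0.77 at 60%.

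**Confounding by era, no true effect.** Take two eras of equal size, a true operated share of 35% in both, late capture of 95%, and recorded re-dislocation of 20% then 30%. Assume also that the listed covariates do not balance year.

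For early capture of 60%:

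- Recorded surgery is 0.35 × 0.60 = 0.21 early and 0.35 × 0.95 = 0.3325 late.
- Surgical risk = (0.21 × 0.20 + 0.3325 × 0.30)/0.5425 = 26.1%.
- Control risk = (0.79 × 0.20 + 0.6675 × 0.30)/1.4575 = 24.6%.
- False hazard ratio = ln(1 − 0.2613)/ln(1 − 0.2458) = 1.07.

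| Early capture | Risks 20% then 30% | Risks 22% then 28% | Risks 30% then 20% |
|---|---|---|---|
| 60% | 1.07 | 1.04 | 0.93 |
| 75% | 1.04 | 1.02 | 0.96 |
| 85% | 1.02 | 1.01 | 0.98 |

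**What each remedy achieves against missed surgery.** Take two equal eras with late capture of 95%.

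- *Early capture 80%, era ignored:* recorded controls are 0.72 and 0.6675, of whom 0.07 and 0.0175 were operated. Contamination is 0.0875/1.3875 = 6.3%.
- *Early capture 80%, matched on era:* (0.28 × 9.7% + 0.3325 × 2.6%)/0.6125 = 5.9%.
- *Late era only:* 0.0175/0.6675 = 2.6%.
- *Early capture 60%:* the same three figures are 10.8%, 8.5% and 2.6%.

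Matching on year removes little contamination, because controls from the same era are affected too. Restriction to the well-linked period removes most of it.

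**The case against.** The strongest reply is that incomplete NHS numbers do not mean missed operations. Appendix F describes two stages. Episodes are first grouped under a HESID, and the second and third routes to that grouping do not use the NHS number. Passes 1 to 5 then link the HESID to CPRD. An early episode without an NHS number can still reach the right patient. The third route was added to raise early linkage, NHS number is reported for 98-99% of CPRD patients, and patients who cannot be linked are excluded.

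This stands as a limit on size. It does not close the point: the same appendix, after describing those routes, still allows lower early efficiency, and linkability is a test on the patient rather than on each episode.

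A reader might infer that capture of surgery is known to have improved, or that it must rise with calendar year. The text says only that efficiency may have been lower. A reader might also construct a larger false effect by letting recorded surgery go from 15% to 35% between eras. At a constant true share of 35%, that needs early capture of 0.15/0.35 = 43% and late capture of 100%, or a real change in surgical practice. The documents support neither, and they document no trend in recorded re-dislocation.

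It can also be said that the updated analysis plan due after Work Package 1 could add year. It could, but Section K uses that stage to confirm which listed factors are reliably collected. The list itself is fixed here without year.

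**Conclusion.** The point holds as a gap in what the protocol fixes: a conceded possibility of weaker early linkage, no calendar bounds, and a pre-specified covariate list without index year. Year becomes a confounder only if recorded surgery and recorded re-dislocation both vary with era. The first is made plausible by Appendix F; the second is an assumption.

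On the assumed ranges the consequences are modest: attenuation from 0.776 to at most about 0.81, and an era effect of about 1.02-1.07, or about 0.93-0.98 if the trend runs the other way. Neither would erase a true effect of the planned size. They matter more if the true effect is nearer 1. The missed-surgery part applies to the fallback control definition; the case for adding year does not depend on which control definition is used.

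**What to change.** - **Sections L and M:** add calendar year of first dislocation to the propensity model, or match within calendar-year bands. The date is already held, so this costs nothing in data.
- **Section I:** require that HES coverage spans the six-month surgery window and the two-year follow-up for every patient. This may remove some patients at the edges of coverage.
- **Sensitivity analysis:** repeat the primary comparison in first dislocations from the period for which Appendix F reports NHS number above 95% complete. Write that period as dates, and report how many operated patients remain. This is the check on missed surgery, since year matching does little for it. It fits better as a sensitivity analysis than as the primary cohort because the loss of operated patients cannot be quantified from the documents.

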Appendix G

TABLE OF CPRD PHYSIOTHERAPY CODES

Description	READ Code
Seen in physiotherapy department	9N1yE00
Physiotherapy	8E...11
Refer to Physiotherapist	8H77.00
Seen in physiotherapy department	9N0F.00
Physiotherapy/remedial therapy	8E...00
In-house physiotherapy	9NJ3.00
Seen by physiotherapist	9N28.00
Refer to Physiotherapist	ZL85.11
Discharge by Physiotherapist	ZLDM.00
Referral to Physiotherapist	ZL85.00
In-house physiotherapy follow up appointment	9NJm.00
Discharge from physiotherapy service	ZLEK.00
Physiotherapy	Z6...00
In-house physiotherapy first appointment	9NJk.00
Physiotherapy manipulation	82D4.00
Physiotherapist	03J1.00
Refer to community physiotherapist	8HHA.00
In-house physiotherapy discharge	9NJI.00
Discharge for hospital physiotherapy service	ZLEK100
Other physiotherapy	8EZ..00
Refer to domiciliary physiotherapy	8HH5.00
Referral to community physiotherapy	ZL85111
Discharge by hospital based physiotherapist	ZLDM200
Discharge by community based physiotherapist	ZLDM100
Private referral to physiotherapist	8HVb.00
In house physiotherapy - domiciliary visit	9NJ4.00
Discharge from community physiotherapy service	ZLEK200
Discharge from community physiotherapist	ZLDM111
Under care of physiotherapy	ZL4A.00
Referral to community based physiotherapist	ZL85100
Discharge by hospital physiotherapist	ZLDM211
Under the care of community physiotherapist	ZL4A111
Referral to hospital based physiotherapist	ZL85200
Under the care of community based physiotherapist	ZL4A100
Referral to hospital physiotherapist	ZL85211
Referral to orthopaedic physiotherapist practitioner	8HI2.00
Seen by intermediate care physiotherapist	9NI9.00
Referred by physiotherapist	9N6B.00
Under the care of hospital physiotherapist	ZL4A211
Under the care of hospital based physiotherapist	ZL4A200
PT -Physiotherapy	Z6...11

